10. SAMPLE SIZE

The sample size estimate outlined below is based on primary endpoint assessment only for the PerQseal® closure device.

The primary endpoint of safety will be assessed by comparison of the proportion of PerQseal® closure device closures with device related major vascular access site complications up to 1 months (P_{safety}) against a performance goal for safety (PG_{safety}) estimated from literature to be 12.5%.

The minimum sample size to demonstrate non-inferiority of safety against the literature based non-inferiority limit of 0.17 (refer to: Section 11.6 Primary Endpoint Analysis) with a one-sided significance level of 0.025 and study power of 90% is estimated to be 68 closures (assuming a 5% major vascular access site complication rate for the PerQseal® closure device). Refer to the independent statistical report for safety sample size in the CIP Appendix F: Independent Statistical Sample Size Report for Safety for details.

A one sided confidence interval is appropriate as the study is only interested in the upper bound of the major complication rate. Each complication will be analysed as a separate event.

Completion of 75 patients is recommended, this number of patients should be sufficient to demonstrate non-inferiority whilst allowing for approximately 10% dropout rate.

For Performance, in order to claim non-inferiority against technical success rate for 'perclose' or 'preclose' technique the lower bound or a (95%) confidence interval for PerQseal® technical success rate must be shown to be greater than the performance non inferiority limit. In order to achieve this, a minimum sample size of 44 closures is required to demonstrate non-inferiority in a single sample fixed one-sided significance level of 0.025 and power of 0.90 level. The secondary performance endpoint therefore does not drive sample size. The total planned sample size remains at 75 treated subjects.

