9.3 Study population

Patients will not be excluded on the basis of age, race, concomitant therapy or co-existing disease. Each centre will continue to enrol eligible patients until a minimum combined Clinical Investigation population of 75 patients is achieved.

Patients with bilateral percutaneous access in the common femoral arteries where both arteries meet all eligibility criteria may, at the discretion of the investigator, both be closed with the PerQseal® closure device. If a PerQseal® is used on the contralateral femoral artery then this will be treated as an independent closure i.e. each limb will be counted as a separate closure only for the purposes of Performance Analysis.

Consented patients who receive contact with the PerQseal[®] closure device become an enrolled subject.

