11. STATISTICAL METHODS

11.1 Analysis populations

All Enrolled subjects (see Section 9.3 Study Population) will be analysed on an Intent-to-Treat (ITT) basis for the Primary and Secondary Endpoint of Safety.

For avoidance of doubt: The ITT analysis population includes all enrolled subjects who undergo attempted access site closure with Vivasure PerQseal® device (i.e. PerQseal® closure device is attempted to be placed into the vasculature and contacted the patient).

All closures from Enrolled subjects will be analysed on a modified Intent-to-Treat (mITT) basis for the Secondary Endpoint of Performance, excluding enrolled subjects which met an exclusion criteria (documented by a protocol deviation).

For avoidance of doubt: The mITT analysis population includes all closures from enrolled subjects who undergo attempted access site closure with Vivasure PerQseal® device (i.e. PerQseal® closure device is attempted to be placed into the vasculature and contacted the patient), with the exception of devices that were prevented from deploying for reasons listed in the exclusion criteria or due to issues associated with the primary procedure.

A secondary analysis population for the primary safety endpoint will include Per-Protocol (PP) for Primary Safety. The PP is a subset of the ITT analysis population with no major protocol deviations and who experienced the safety endpoint or did not prematurely withdraw from the study prior to being evaluated for the primary safety endpoint.

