11.5 Variables

The study variables identified for comparisons/summaries are:

Primary Variables:

- i. Major device related vascular access site complication rate.
- ii. Serious Adverse Device Effect (SADE), Unanticipated Serious Adverse Device Effect (USADE) rate, as defined in the 'Clinical Investigation Definitions' (which is maintained in the Site File for each site).

Secondary Variables

- i. Safety: minor vascular access site complications related to the closure.
- ii. Adverse Device Effect (ADE), Serious Adverse Event (SAE) or Adverse Event (AE) rate, as defined in the 'Clinical Investigation Definitions'.

Performance: assessed by technical success rate for the PerQseal® closure device.

The potential influencing variables identified include:

- i. Patient age, gender, weight or Body Mass Index (BMI)
- ii. ACT
- iii. Co-existent diseases
- iv. Sheath size used
- v. Common Femoral Artery (CFA) diameter
- vi. Procedure to be performed

11.6 **Primary endpoint analysis**

The Safety of the PerQseal® closure device will be assessed by comparison of the proportion of PerQseal® closure device subjects with device related major vascular access site complication up to 1 months (P_{safety}) against a performance goal for safety (PG_{safety}). (The performance goal for safety for this study will be based on historical data extracted from literature for cut-down and suture closure.)

This will be achieved by testing for non-inferiority against a safety non-inferiority limit (N_{LS}), which is the predetermined PG_{safety} plus a non-inferiority margin delta. In order to claim non-inferiority against a safety driven PG_{safety} the upper bound of a one-sided (95%) confidence interval for the proportion of subjects with complications " P_{safety} " (using the exact method for estimating a Binomial proportion) must be shown to be less than the non-inferiority limit.

The PG_{safety} and non-inferiority margin delta have been derived from a Meta-analysis of major vascular access site complication rates for cut-down and suture closure from equivalent patient populations and sheath sizes of 12 - 24 F reported in the literature:

The proportion of complications is estimated to be 0.125 with a 95% Confidence Interval of 0.09 to 0.17. Given that the upper bound is 0.17 this justifies the use of 0.13 as valid PG_{safety} plus a non-inferiority margin of 0.04 yielding an overall non-inferiority limit (N_{LS}) of 0.17 for Safety.

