The test for non-inferiority for safety will be based on a one-sided test (at the 0.025 significance level) for a binomial proportion with hypotheses:

 H_{0S} : $P_{safety} \ge N_{LS}$ versus H_{1S} : $P_{safety} < N_{LS}$

Where: P_{safety} is the actual proportion of subjects with device related major vascular access site complications within the analysis population (ITT and PP).

And: N_{LS} is the non-inferiority limit for proportion of expected major vascular access site complications associated with cut-down and suture closure.

Non-inferiority analysis will be done by using the study data to calculate a confidence interval for the population proportion with major vascular access site complications directly related to the device. Demonstrating non-inferiority for safety necessitates rejecting the null hypothesis (H_{0S}) in favour of the alternative hypothesis (H_{1S}), in this case based on the upper limit of a 95% confidence interval for a population proportion being less than the non-inferiority limit.

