11.10 Missing data

Historically (which includes 120 subjects and 136 closures across all Frontier studies) there have not been any device related access site complications beyond patient discharge from hospital. So it is expected that all safety data will be captured for all enrolled subjects. All subjects with available data will be used in the statistical analyses. All implanted subjects will be assessed for technical success. With regard to assessment of device related complications through 1 months, data on all subjects through the point of last follow up prior to or at 1 months will be included in the analysis. For the primary analysis, no imputation is expected to be performed for missing data. However, in the unlikely event that there is missing critical safety data Bayesian models may be utilised for sensitivity to investigate the impact of incomplete follow-up.

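### The stated minimum of 68 closures gives 87.6% power, not 90%, under the exact one-sided 0.025 test; the smallest number reaching 90% is 74

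*SAP*

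**What the plan says.** The protocol's sample size section and SAP 10 give the same statement: the minimum, "with a one-sided significance level of 0.025 and study power of 90% is estimated to be 68 closures", for a 5% true rate and a non-inferiority limit of 0.17. Both then recommend 75 patients to cover about 10% dropout. SAP 10 refers to CIP Appendix F for the derivation; that appendix is not among the public documents.

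SAP 11.6 describes the analysis in two ways. One paragraph requires that "the upper bound of a one-sided (95%) confidence interval for the proportion of subjects with complications", obtained "using the exact method for estimating a Binomial proportion", lie below the limit. A later paragraph says: "The test for non-inferiority for safety will be based on a one-sided test (at the 0.025 significance level"). The closing paragraph of 11.6 refers to the upper limit of a 95% interval without saying whether it is one-sided or two-sided.

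On populations, SAP 11.1 says enrolled subjects "will be analysed on an Intent-to-Treat (ITT) basis for the Primary and Secondary Endpoint of Safety" and adds a per-protocol set as a secondary population. SAP 11.6 names both sets for the test, which concerns the proportion with "device related major vascular access site complications within the analysis population (ITT and PP"). On incomplete follow-up, SAP 11.10 says "data on all subjects through the point of last follow up prior to or at 1 months will be included in the analysis".

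On the unit, SAP 10 counts closures and SAP 11.6 counts subjects. SAP 9.3 says that for bilateral cases "each limb will be counted as a separate closure only for the purposes of Performance Analysis".

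**The concern.** A sample size is tied to the test it is meant to support. With few expected events, the exact binomial test moves in whole events: the number allowed stays fixed over a range of sample sizes and then steps up by one. A number from a smooth approximation can therefore miss its stated power under the exact test. If 68 is not enough, the argument that 75 patients can lose about 10% and still have 90% power also fails.

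The two confidence levels in SAP 11.6 are a related problem. A one-sided 95% bound is a test at 0.05, not 0.025. The study is unblinded and has a single arm, and one event can separate success from failure, so the success rule should have only one reading before results are known.

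**Working it through.** **Inputs.** Limit p0 = 0.17, true rate p1 = 0.05, one-sided alpha 0.025, power 90%, stated minimum 68, planned 75, dropout about 10% (SAP 10; all but the unit are repeated in the protocol). Method: exact binomial (SAP 11.6).

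**Step 1: trying to reproduce 68.** With z = 1.960 for alpha and 1.2816 for power:

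- Arcsine: n = [(1.960 + 1.2816) / (2(arcsin√0.17 − arcsin√0.05))]² = 66.02, so 67. Its nominal power at 68 is 90.8%.
- Normal score: n = [(1.960·√(0.17·0.83) + 1.2816·√(0.05·0.95)) / 0.12]² = 71.62, so 72; with a continuity correction, 80.

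None gives exactly 68; the arcsine formula is closest. The score formula would give 68 if the limit were an unrounded 0.174, which is an assumption.

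**Step 2: the exact test.** Let c be the largest count with P(X ≤ c | n, 0.17) ≤ 0.025. Then power = P(X ≤ c | n, 0.05). This is the same rule as requiring the exact one-sided 97.5% upper bound to lie below 0.17.

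For n = 68: P(X ≤ 5 | 0.17) = 0.0180 and P(X ≤ 6 | 0.17) = 0.0434, so c = 5. Power = P(X ≤ 5 | 0.05) = 0.8758. As a check, the 97.5% upper bound is 16.3% for 5/68 and 18.2% for 6/68.

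| n | Events allowed | Exact size | Power |
|---|---|---|---|
| 67 | 5 | 0.0203 | 88.2% |
| 68 | 5 | 0.0180 | 87.6% |
| 69 | 5 | 0.0160 | 86.9% |
| 73 | 5 | 0.0099 | 84.2% |
| 74 | 6 | 0.0228 | 92.3% |
| 75 | 6 | 0.0204 | 91.9% |
| 79 | 6 | 0.0130 | 89.99% |
| 80 | 6 | 0.0116 | 89.5% |
| 81 | 7 | 0.0250 | 95.1% |

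No n below 74 reaches 90%. Above 74, only 79 and 80 fall below it (checked to n = 399).

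Rounding of the limit does not explain the gap. For any limit from 0.165 to 0.1749, 68 still allows 5 events and gives 87.6%; the exact minimum then runs from 76 down to 72.

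**Step 3: after dropout.** 75 × 0.90 = 67.5. With 67 or 68 analysed, power is 88.2% or 87.6%. Smaller losses can be worse: 69 to 73 analysed give 86.9% down to 84.2%, because 5 events remain the maximum.

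**Step 4: the other confidence level.** At one-sided 0.05, 68 allows 6 events (power 94.7%) and 75 allows 7 (96.6%, exact size 0.0460). For 7 events in 75:

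- one-sided 95% upper bound 16.8%, below 17%: non-inferior;
- one-sided 97.5% upper bound 18.3%, above 17%: not shown.

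For 6 in 75 the 97.5% bound is 16.6%, so both rules pass.

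**The case against.** **The figure may be an approximation, not a slip.** SAP 10 calls 68 an estimate and points to an appendix that cannot be seen here, and an arcsine calculation comes within one of it. That is a fair account of where 68 may come from. It does not give 68 its stated power under the exact method in SAP 11.6; it means the sizing and the analysis do not match.

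**Enrolment and the main analysis are unaffected.** This stands. The intention-to-treat set keeps every enrolled subject up to last follow-up, 75 subjects give 91.9%, and the SAP does not promise 90% power for the per-protocol set. But SAP 10 justifies 75 as a minimum plus a dropout allowance, and that justification is wrong as written. The real reserve at 75 is one subject.

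**Counted in closures, there may be no shortfall.** SAP 11.10 reports 136 closures in 120 earlier subjects. If that ratio held here (an assumption), 75 patients would give 75 × 136/120 = 85 closures (power 93.8%), or about 76 after 10% loss (91.4%), treating limbs as independent. The protocol's study design section also counts each limb separately without restriction. However, SAP 11.6 defines the tested proportion in subjects, and SAP 9.3 confines the limb count to performance. Subjects are the better-supported unit, and the conflict itself needs settling.

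**The confidence-level conflict matters more than 2.4 points of power.** For a result such as 7 of 75 it does. The one-sided 95% bound would also lift 68 above 90%, but only by giving up the 0.025 stated in the protocol, SAP 10 and SAP 11.6.

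**Conclusion.** The concern holds. Under the exact binomial test at one-sided 0.025, with a 5% true rate and a limit of 0.17, 68 gives 87.6% power, 2.4 points below the stated 90%. The smallest number that reaches 90% is 74, at 92.3%. The planned 75 meets the target at 91.9% if all subjects are analysed. With 67 to 73 analysed, power is between 88.2% and 84.2%.

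The two success rules in SAP 11.6 disagree at 7 events in 75. Taking the one-sided 95% bound literally gives an actual type I error of 4.6% at that size, against the stated 2.5%.

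These figures assume independent units, one binary outcome per subject, and 0.025 as the intended level. How 68 was derived cannot be established from the documents. This should be corrected, but it does not call for a larger study.

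**What to change.** 1. **Protocol sample size section and SAP 10.** Replace the 68-closure statement with wording such as: *74 analysed subjects give at least 90% power (92.3%; non-inferiority if at most 6 subjects have an event) under the exact binomial test at one-sided 0.025, with a true rate of 5% and a limit of 0.17. With 75 subjects in the ITT analysis the power is 91.9%. If 67 to 68 subjects are analysed, for example in the per-protocol set after about 10% loss, the power is about 88%.* Note that 79 and 80 fall just below 90%. It would help to add that 69 to 73 analysed subjects give 86.9% down to 84.2%.
2. **SAP 11.6.** Replace the one-sided 95% interval with a one-sided 97.5% exact upper bound (the upper limit of the two-sided 95% exact interval), so that it agrees with the 0.025 test.
3. **Unit.** Use subjects in SAP 10, as in SAP 11.6. The sentence in both documents that treats each complication as its own event should be reconciled with a proportion of subjects.

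The cost is text only, with no added subjects. The sponsor accepts a less favourable power figure at 68 and gives up the more lenient reading, so 7 of 75 would no longer count as success.

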Dipyridamole	xx.x (xx/xx)
Abciximab	xx.x (xx/xx)
Tirofiban	xx.x (xx/xx)
Eptifibatide	xx.x (xx/xx)
Other	xx.x (xx/xx)

Table 22. Adverse events / complications summary (CRF data)

	n	
Subjects with non-serious adverse events		
Up to and including haemostasis procedure	xx	
Up to and including discharge	xx	
Up to and including 1 month	xx	
Up to and including 3 month	xx	
Subjects with serious adverse events		
Up to and including haemostasis procedure	xx	
Up to and including discharge	xx	
Up to and including 1 month	xx	
Up to and including 3 month	xx	
Deaths		
Up to and including haemostasis procedure	xx	
Up to and including pre-discharge	xx	
Up to and including 1 month	xx	
Up to and including 3 month	XX	

Table 23. Protocol deviations summary

	Total number of	% (n/N) of subjects
	deviations	with deviations
Subject did not sign informed consent/	XX	xx.x (xx/xx)
inadequate consent process		
Subject did not meet inclusion/exclusion criteria	xx	xx.x (xx/xx)
Follow-up/assessment not completed		
Baseline	XX	xx.x (xx/xx)
Procedure	XX	xx.x (xx/xx)
Discharge	XX	xx.x (xx/xx)
1 month	XX	xx.x (xx/xx)
3 month	XX	xx.x (xx/xx)
Follow-up/assessment not performed according to		
the protocol		
Baseline	XX	xx.x (xx/xx)
Procedure	XX	xx.x (xx/xx)
Discharge	XX	xx.x (xx/xx)
1 month	XX	xx.x (xx/xx)
3 month	XX	xx.x (xx/xx)
Follow-up/assessment out of window		
Baseline	XX	xx.x (xx/xx)
Procedure	XX	xx.x (xx/xx)
1 month	XX	xx.x (xx/xx)
3 month	XX	xx.x (xx/xx)
AE/SAE reporting		
Procedure	XX	xx.x (xx/xx)
Discharge	XX	xx.x (xx/xx)
1 month	XX	xx.x (xx/xx)
3 month	XX	xx.x (xx/xx)
Other		
Baseline	XX	xx.x (xx/xx)
Procedure	XX	xx.x (xx/xx)
Discharge	XX	xx.x (xx/xx)
1 month	xx	xx.x (xx/xx)
3 month	XX	xx.x (xx/xx)

Table 24. Summary of major vascular access site complication types up to 1 months

	subjects with
	complication
Access site related major vascular complications leading to death, life-	XX
threatening (BARC type 5) or major bleeding (BARC type 3a), visceral	
ischemia or neurological impairment	
Distal embolization from the vascular access site requiring surgery or resulting	xx
in amputation or irreversible end-organ damage	
The use of unplanned endovascular or surgical intervention associated with	xx
access site related death, major bleeding (BARC type 3a), visceral ischemia	
or neurological impairment	
Any access site related new ipsilateral lower extremity ischemia documented	xx
by patient symptoms, physical exam, and/or decreased or absent blood flow	
on lower extremity angiogram	

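### The protocol and SAP 10 say each major complication is a separate event, but the SAP 11.6 primary test is an exact binomial on subjects; the count-once rule should be stated

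*SAP*

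**What the plan says.** The counting sentence, "Each complication will be analysed as a separate event", appears in the protocol under Sample Size and again in SAP 10. In both places it follows a remark about the upper bound of the major complication rate, in text that is limited to the primary endpoint.

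SAP 11.6 sets out the primary analysis as a "comparison of the proportion of PerQseal® closure device subjects with device related major vascular access site complication up to 1 months" with a performance goal. The decision rule is an upper confidence bound, "using the exact method for estimating a Binomial proportion) must be shown to be less than the non-inferiority limit". The hypotheses define P_safety as the "actual proportion of subjects with device related major vascular access site complications within the analysis population (ITT and PP"). The limit is given as "yielding an overall non-inferiority limit (N_{LS}) of 0.17 for Safety".

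SAP 10 uses a different unit for the same quantity, the "proportion of PerQseal® closure device closures with device related major vascular access site complications up to 1 months". SAP 9.3, however, restricts per-limb counting to the performance analysis.

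The major-complication definition (protocol Definitions; SAP 4.2) is a list of seven items, any of which qualifies. Table 24 in SAP 16.1 counts subjects by complication type. Table 2 shows the primary result as a percentage with n/N and does not define n. Neither document says that a subject with more than one qualifying complication counts once.

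**The concern.** An exact binomial interval assumes that each unit contributes zero or one to the numerator. If complications are counted as separate events while subjects remain the denominator, one subject can contribute more than one. Events within a subject are also not independent, so the interval and the power figure no longer describe the quantity being tested.

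Several components can arise from one clinical episode. For example, a complication that leads to major bleeding can also fall under the item that begins "The use of unplanned endovascular or surgical intervention associated with" access-site death or major bleeding.

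Only a handful of failures are allowed, so the counting rule can decide the result. In a single-arm, unblinded study, a numerator that can be read in two ways could also be settled after the events are known.

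**Working it through.** **Inputs.** Limit 0.17, assumed device rate 0.05, one-sided 0.025, 90% power and 68 closures (SAP 10 and 11.6); 75 patients planned (SAP 8 and 10). SAP 11.6 also describes a one-sided 95% bound, so both levels are shown. The number of complications per affected subject is not in the documents and is assumed.

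**1. The plan's own figure.** The arcsine formula is n = [(z₀.₉₇₅ + z₀.₉₀) / (2(arcsin√0.17 − arcsin√0.05))]² = [3.2415 / (2 × (0.42499 − 0.22551))]² = 66.02, rounded up to 67. This is within one of the stated 68. The exact test at n = 68 allows 5 failures and has 87.6% power. At n = 75 it allows 6 and has 91.9%. All of these take one yes/no outcome per unit.

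**2. Failures allowed at n = 75.** The exact upper bound for x failures is the 1 − α quantile of Beta(x + 1, n − x).

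| x of 75 | α = 0.025 | α = 0.05 |
|---|---|---|
| 4 | 0.131 | 0.118 |
| 6 | 0.166 | 0.152 |
| 7 | 0.183 | 0.168 |
| 8 | 0.199 | 0.184 |

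Against 0.17, the maximum is 6 at the 0.025 rule and 7 under the one-sided 95% wording.

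**3. Same data, two counts.** Suppose four subjects are affected, one with four separately counted complications and three with one each.
- By subject: 4/75, bound 0.131, pass.
- By event: 4 + 3 = 7. At the 0.025 rule the bound is 0.183, fail. Under the one-sided 95% wording it is 0.168, pass.

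**4. Chance of passing at a 5% subject rate.** Let K ~ Bin(75, 0.05) be the affected subjects. Let a fraction q of them have two events, so the extra events are E ~ Bin(K, q). The trial passes if K + E ≤ 6. Three or fewer affected subjects always pass: P(K ≤ 3) = 0.0213 + 0.0843 + 0.1641 + 0.2101 = 0.4798. Also P(K = 4) = 0.1991, P(K = 5) = 0.1488 and P(K = 6) = 0.0914.

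For q = 0.5: 0.4798 + 0.1991 × 0.6875 + 0.1488 × 0.1875 + 0.0914 × 0.0156 = 0.646.

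| Affected subjects with two events | At most 6 (0.025 rule) | At most 7 (one-sided 95%) |
|---|---|---|
| none (subject count) | 91.9% | 96.6% |
| 10% | 86.3% | 93.0% |
| 20% | 80.7% | 88.9% |
| 50% | 64.6% | 75.1% |
| all | 48.0% | 48.0% |

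**5. Direction of the error.** With subjects as denominator, K + E ≥ K, so any data set that passes by events also passes by subjects. At a true subject rate of 0.17 and the 0.025 rule, the chance of passing is 2.04% counting subjects, 1.40% at q = 0.1, 0.31% at q = 0.5 and 0.06% at q = 1. The false-positive rate falls.

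**The case against.** The strongest reply is that SAP 11.6 is the section that governs the primary analysis and already works per subject. SAP 10 refers to it, SAP 11.1 defines the safety population as enrolled subjects, and Table 24 counts subjects. A statistician who follows 11.6 alone counts each patient once. That stands, and it lowers the likelihood of harm. It does not remove the conflict, because the sentence sits in primary-endpoint text in both documents and nothing limits it to descriptive use.

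A reader might infer that every criterion met becomes its own failure, so that one rupture scores several times. The documents do not say so: the sentence speaks of each complication, and the definition can be read as one complication that qualifies in several ways.

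A reader might also infer that one patient would typically use up most of the allowance. At n = 75 that takes at least four separately counted complications out of six allowed; at n = 68 it takes three of five. A patient with two uses a third of the six.

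Finally, a reader might fear that an unsafe device could pass. With subjects as denominator, event counting only adds failures, so it cannot cause that.

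The protocol supplied is a synopsis, and the sample-size report that SAP 10 cites (CIP Appendix F) is not among the documents. Clarifying wording may exist there.

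**Conclusion.** The conflict is real and of moderate severity. A stated counting rule for complications does not fit the binomial test of subjects, and the reviewed text does not say which prevails.

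If the separate-event rule were applied to the primary numerator at n = 75 and a 5% subject rate, the chance of passing at the 0.025 rule would drop from 91.9% to about 86%, 81%, 65% or 48%, for 10%, 20%, 50% or all affected subjects with two events. Under the one-sided 95% wording the 50% case is about 75%. These figures rest on assumed multiplicities, on no subject having more than two events, and on subjects as denominator.

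The consequences are lost power, an invalid binomial model and a numerator left open to choice. The false-positive rate is not inflated. SAP 11.6 read alone gives the correct count.

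**What to change.** Delete the separate-event sentence from the protocol's sample-size text and from SAP 10. In its place, state that a subject with one or more qualifying device-related major complications up to 1 month counts once in the primary numerator. Add that individual complications are tabulated by type in Table 24, where a subject may appear in more than one row.

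At the same revision, change the unit of P_safety in SAP 10 from closures to subjects, so that it matches SAP 11.6.

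The cost is a few sentences across the two documents. No new data, visits or analyses are needed, and the planned 75 patients can stay: the exact test on subjects at n = 75 has 91.9% power at the 0.025 rule.
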